4 STUDY DRUG

Triheptanoin is a medium chain triglyceride (MCT) that can improve mitochondrial function and energy production and therefore has potential for slowing ALS progression (reviewed in reference 3). Indeed, triheptanoin slowed motor neuron loss and delayed the onset of weakness in a mutant SOD1 model of ALS (4). The Triheptanoin we will use is a colorless to light yellow oil. The target triheptanoin dose for this study is 1g/kg/d. This target dose was selected because it was safe and tolerable and altered brain MR spectroscopy in patients with Huntington's Disease (10). Participants will taper up to this dose as follows: start at 0.25g/kg/d for 1 week, then take 0.5g/kg/d for 1 week, then take 1g/kg/d and stay on this dose for the duration of the study. Triheptanoin will be administered orally with food or by gastrostomy tube over 3 divided doses (breakfast, lunch, and dinner). If at any point after week 1 a participant does not appear to be tolerating their current dose, it will be reduced by 0.25g/kg/d. If they cannot tolerate the starting dose of 0.25g/kg/d, the treatment will be discontinued. A dietician will make contact with all participants every month, either in person or by telephone, to try and maximize compliance.

Additional details about this drug are available in the accompanying IB.

5 SAFETY & ADVERSE EVENTS

5.1 Adverse Events Monitoring

All adverse events (AEs), whether observed by the Investigator, elicited from the participant or volunteered by the participant, and whether ascribed to the drug or not, will be recorded. This will include the following: a brief description of the event, the date of onset, the date of resolution, the duration and type of the event, the severity, contributing factors and any action taken with respect to the study drug. This recording will commence following informed consent, and with the initiation of protocol-specific procedures and continue at each study visit or telephone contact until 4 weeks following the last study related visit.

For each adverse event, the relationship to the study drug will be recorded as one of the choices on the following scale:

DEFINITE Causal relationship is certain (i.e., the temporal relationship between drug exposure and the adverse event onset/course is reasonable, there is a clinically compatible response to de-challenge, other causes have been eliminated and the event must be definitive pharmacologically or phenomenologically using a satisfactory re-challenge procedure if necessary).

PROBABLE High degree of certainty for causal relationship (i.e., the temporal relationship between drug exposure and the adverse event onset/course is reasonable, there is a clinically compatible response to de-challenge [re-challenge is not required] and other causes have been eliminated or are unlikely).

POSSIBLE Causal relationship is uncertain (i.e., the temporal relationship between drug exposure and the adverse event onset/course is reasonable or unknown, de-challenge/re-challenge information is either unknown or equivocal and while other potential causes may or may not exist, a causal relationship to the study drug does not appear probable).

UNLIKELY Not reasonably related, although a causal relationship cannot be ruled out (i.e., while the temporal relationship between drug exposure and the adverse event onset/course does not preclude causality, there is a clear alternate cause that is more likely to have caused the adverse event than the study drug).

NOT RELATED No possible relationship (i.e., the temporal relationship between drug exposure and the adverse event onset/course is unreasonable or incompatible, or a causal relationship to study drug is implausible).

The severity of each adverse event must be recorded as one of the choices on the following scale:

MILD	No limitation of usual activities
MODERATE	Some limitation of usual activities
SEVERE	Inability to carry out usual activities

The expectedness of an AE must be indicated when reporting adverse events. An unexpected adverse event is any adverse experience for which the specificity or severity of the event is not consistent with the current IB.

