3.5.2 Secondary Outcome Measures

Secondary outcome measures include:

MR Spectroscopy NAA/Cr ratio in motor cortex will be measured at screening/baseline and 1 month time points. This measure declines over time in patients with ALS (14-17). This measure can respond to treatment; it was shown to improve over 3 weeks in patients with ALS on riluzole compared to a group that was not on this treatment (18). We will compare the MR spectroscopy changes over 1 month in Group 1 to the MR spectroscopy changes over 1 month in Group 2.

A Serum and Urine Biomarker Panel will be obtained at screening/baseline, 1 month and 6-month time points and analyzed using liquid chromatography/tandem mass spectrometry. Laboratory, pathologic, and epidemiologic evidence clearly supports the hypothesis that oxidative stress is central in the ALS pathogenic process, particularly in genetically susceptible individuals (19). Oxidative stress biomarkers in cerebrospinal fluid, plasma, and urine are elevated, suggesting that abnormal oxidative stress is generated outside of the central nervous system. Magnitude of lipid peroxidation, measured as non-enzymatic oxidation products of arachidonic acid, F2-isoprostanes, appears the most obvious oxidative stress marker. We will measure urine F2-isoprostane metabolites (class III: iPF2 α -III, and 2,3-dinor iPF-2 α -III, class VI: iPF-2 α -VI, and 8,12-iso-iPF-2 α -VI), urine creatinine, and serum and urine glutamate, α -keto-glutarate, NADH, coenzyme A levels in all treated participants and healthy controls at screening/baseline, month 1 and month 6 time points. We will compare the biomarker changes at different time points between Groups 1, 2 and 3.

For safety monitoring: concomitant medications, vital signs, weight, physical exam and safety labs (CBC, CMP, Lipid Profile, GGT, LFT and pregnancy testing for sexually active females with child bearing potential) will be measured at screening/baseline, 1 month, 3 month, and 6-month time points. Adverse events will be monitored continuously throughout the study, as described in Section 5.1.

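### An asymptomatic laboratory abnormality recorded as an adverse event can only be graded MILD, so severity summaries can understate laboratory toxicity

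*Combined protocol and SAP*

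**What the plan says.** Section 5.1 has the site record every adverse event by whatever route it comes to light: "All adverse events (AEs), whether observed by the Investigator, elicited from the participant or volunteered by the participant". It then makes a severity grade compulsory: "The severity of each adverse event must be recorded as one of the choices on the following scale". The scale has three levels:

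- MILD: "No limitation of usual activities"
- MODERATE: "Some limitation of usual activities"
- SEVERE: "Inability to carry out usual activities"

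Section 3.5.2 lists the laboratory part of safety monitoring as "safety labs (CBC, CMP, Lipid Profile, GGT, LFT and pregnancy testing for sexually active females with child bearing potential". Both that section and Table 1 schedule these tests at screening/baseline and months 1, 3 and 6. No section gives a toxicity grade, a clinical-significance threshold or a second severity scale for laboratory results. No section says when an abnormal result becomes an adverse event.

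Expectedness is defined twice. Section 5.1 says: "An unexpected adverse event is any adverse experience for which the specificity or severity of the event is not consistent with the current IB". Section 5.1.1 decides it only by whether the event is listed in the Investigator's Brochure (IB).

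**The concern.** Safety and tolerability come first in the stated purpose (Section 1.1) and are secondary hypothesis 3 (Section 1.3). Section 3.1 notes that the drug has not been studied in people with ALS. The study drug is a triglyceride oil with a target of 1 g/kg/d, and the protocol chose lipid and liver tests as part of its safety panel. These measurements can move a long way without the participant noticing anything.

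A scale that asks only about activities cannot separate a small change in them from a large one. The plan does more than leave laboratory severity unspecified: it imposes a rule that gives small and large findings the same, lowest grade. A reader of a table of adverse events by severity would see only MILD entries for asymptomatic laboratory findings and could take that as reassurance. Section 3.6 plans no laboratory analysis that would correct the impression.

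**Working it through.** The plan states no figure to reproduce on this point. The check is a reading of the rule, followed by a count of the panels it could touch.

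**Step 1: apply the scale to an asymptomatic laboratory finding.** Suppose a result is recorded as an adverse event and limits no activity.

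- SEVERE needs the participant to be unable to carry out activities: not met.
- MODERATE needs some limitation: not met.
- MILD needs none: met.

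The size of the result enters none of the three definitions. As an illustration only, transaminases at 2 times and at 15 times the upper limit, both without symptoms, receive the same grade.

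**Step 2: look for another rule that would change this.**

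| Place | What it covers | Grades laboratory size? |
|---|---|---|
| Section 3.4, Table 1 | When tests are done | No |
| Section 3.5.2 | Which tests are done | No |
| Section 3.6 | ALSFRS-R slope and its power | No |
| Section 5.1 | Causality, severity, expectedness | Activity scale only |
| Section 5.1.1 | Seriousness and reporting | No; seriousness is judged separately |
| Section 5.2 | Oversight | No |

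Nothing overrides Step 1. It does carry a condition: the finding must first be recorded as an adverse event, and the plan does not say when that happens.

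**Step 3: count the exposed panels.** Inputs: 5 participants in each of Groups 1 and 2 (Section 3.1); safety laboratories at baseline and months 1, 3 and 6 (Table 1); Group 1 has standard care alone for the first month, and Group 2 starts drug at baseline (Sections 3.1 and 3.3).

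- All scheduled panels: 10 × 4 = 40
- Baseline panels, before drug: 10 × 1 = 10
- Group 1 month-1 panels, at the end of standard care alone: 5 × 1 = 5
- Scheduled on-drug panels: 40 − 10 − 5 = 25

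Check by group: Group 1, months 3 and 6, 5 × 2 = 10; Group 2, months 1, 3 and 6, 5 × 3 = 15; total 25.

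Table 1 schedules no safety laboratories in the extension, and Table 2 schedules none for the healthy controls. The 25 is an upper limit, because a participant who stops the drug may stay in the study off treatment (Section 5.2).

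**Step 4: see what uses the grade.** Hypothesis 3 sets no severity criterion. Section 3.6 specifies no adverse event analysis. Section 5.2 states that there are no formal stopping rules. The seriousness criteria in Section 5.1.1 do not refer to the grade. What remains is the descriptive severity label, and possibly the expectedness judgement under the Section 5.1 definition.

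**The case against.** The strongest reply is that the label carries little weight. The numeric values are collected as safety data in their own right, and with 10 treated participants every value can be listed. Section 5.1.1 makes a medically important event an SAE whatever its severity grade, has SAEs reported to the IRB within 24 hours of recording, and treats events of doubtful seriousness as SAEs. Section 5.2 has the investigator review all adverse events, not only those above some grade. A marked liver or lipid abnormality would therefore not vanish from the record.

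All of this stands, and it limits the point to reporting. It does not remove it. Seriousness and severity are separate attributes, so an SAE could still carry the grade MILD. A marked abnormality that is not serious has no other severity descriptor. The plan includes no shift table or grading of the raw values.

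Three stronger readings are tempting, and the documents do not support them.

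- A reader might infer that toxicity is understated in a safety endpoint, or that the lack of a DSMB makes a low grade dangerous. No endpoint or decision rule uses the grade.
- A reader might infer that an event graded MILD could never count as more severe than the IB describes. Section 5.1 does not say that the comparison uses the recorded category, a laboratory value can be compared with the IB directly, and Section 5.1.1 goes by listing alone. The IB is also not among the documents.
- A reader might infer from the starting scores of 2 to 40 in Section 3.6 that participants will be so disabled that the activity scale mainly tracks ALS. That range is a simulation assumption for the power table, not an entry criterion.

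**Conclusion.** The point holds as a modest safety-reporting defect. By the wording of Section 5.1, an asymptomatic laboratory abnormality recorded as an adverse event must be graded MILD whatever its size, so a severity summary used to support hypothesis 3 can understate laboratory toxicity.

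The exposure is at most 25 scheduled on-drug panels. How many would contain a misgraded event cannot be estimated, because the documents give no rate of laboratory abnormalities. The conclusion assumes that at least some laboratory findings will be recorded as adverse events, that the scale is applied as written, and that adverse events will be summarised by severity, which is usual but not specified here. The primary ALSFRS-R analysis is unaffected.

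The two definitions of expectedness are a separate, smaller inconsistency: one brings in severity and the other does not.

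**What to change.** In Section 5.1:

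1. State when a laboratory abnormality is recorded as an adverse event.
2. Grade laboratory adverse events on a numeric toxicity scale (for example CTCAE), using the values already collected, and keep the activity scale for symptomatic events.
3. Prespecify a descriptive summary of the worst on-drug grade for each laboratory parameter against the participant's own baseline. For Group 1, the month-1 panel precedes drug and does not count as on-drug.
4. Reconcile the expectedness definitions in Sections 5.1 and 5.1.1, so that it is clear whether severity is part of the test.

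The cost is wording and one CRF field, with no new tests or visits. The downside is that some events now called MILD will carry higher grades. The change is best made before any grades are assigned, so that all participants are graded in the same way.

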5.1.1 Reporting of Serious Adverse Events

A serious adverse drug event (SAE) is defined as any adverse event that occurs during the study that results in any of the following outcomes: death, a life-threatening adverse event (i.e., the participant was at immediate risk of death from the event as it occurred; does not include an event, that had it occurred in a more severe form, might have caused death), inpatient hospitalization or prolongation of existing hospitalization (hospitalizations scheduled before enrollment for an elective procedure or treatment of a pre-existing condition which has not worsened during

participation in the study will not be considered a serious adverse event), a persistent or significant disability/incapacity (substantial disruption of one's ability to conduct normal life functions), a congenital anomaly/birth defect, a medically important event or required medical intervention to avoid one of the above outcomes. In addition to the above procedures for AEs, all SAEs will be reported to the IRB within 24 hours of recording. All serious adverse event information will be followed until resolution or an appropriate end point is reached. This may involve contacting other clinicians responsible for the participant's care to obtain information on diagnoses, investigations performed and treatment given.

Institution and Sponsor-Investigator are responsible for the identification, collection, reporting and documentation of SAEs in patient(s) participating in the Protocol. Institution and Sponsor-Investigator are responsible for complying with all Applicable Laws concerning the reporting of Suspected Unexpected Serious Adverse Reactions (SUSARs) to the IRB and regulatory authorities (FDA), in accordance with 21 CFR 312.32, in connection with the Protocol. Notwithstanding the foregoing, Institution and Sponsor-Investigator shall comply with IRB reporting instructions and all Applicable Laws regarding SAE reporting.

The Sponsor-Investigator shall collect AEs and SAEs for patient(s) receiving Investigational Product at the Institution as per protocol. Sponsor-Investigator shall record seriousness, causality and expectedness assessments for each AE as per Institution's policies. All SAEs provided to Ultragenyx must have the Sponsor-Investigator's assessment of seriousness, causality and expectedness. Events not listed in the Investigator Brochure (IB) are considered "unexpected" and events listed in the IB are considered "expected." The Institution and/or Sponsor-Investigator is responsible for determining the reportability of each assessed SAE. All SAEs considered by the Sponsor-Investigator as unexpected per the IB, and Investigational Product related, must be reported as a SUSAR by the Sponsor-Investigator to the FDA and IRBs in accordance with Applicable Laws.

All SUSARs shall be reported to FDA and Ultragenyx by completing and submitting MedWatch 3500A form. Safety reports must be as complete as possible, at minimum including the SAE term(s), patient identifier, seriousness criteria, date of event onset, causality and expectedness assessment between each reported SAE term and Investigational Product, and name of the reporter (Sponsor-Investigator). Information not available at the time of the initial report shall be documented on a follow-up report and submitted to Ultragenyx (and/or regulatory authorities, IRBs, accordingly) as specified in [Table 4](#). Additional information shall include SAE stop date(s), outcome for each reported SAE, dates when Investigational Product was first received and the last dose prior to event onset, and action taken with Investigational Product as a result of the SAE. If applicable, the Institution and/or Sponsor-Investigator protocol number shall be included in all MedWatch Form 3500A or CIOMS I reports.

SAEs with fatal and/or life-threatening outcomes occurring during treatment, regardless of causality or expectedness shall be reported to Ultragenyx within 7 calendar days of event knowledge. In addition, SAEs meeting SUSAR criteria, as defined by Applicable Laws and regulations, occurring during treatment, shall be reported to FDA and Ultragenyx within 15 calendar days of event knowledge. The Sponsor-Investigator must also notify the IRB of the SAEs in accordance with IRB requirements and Applicable Laws and regulations.

Institution and/or Sponsor-Investigator shall submit all initial and follow-up SUSAR reports to the FDA, IRBs, and Ultragenyx within regulatory defined timeframes. Final versions of the initial fatal and/or life-threatening SUSAR reports will be submitted as soon as possible but no later than 7-calendar days of first knowledge of the event, and follow-up information will be submitted within an additional 8-calendar days to the FDA, IRB and Ultragenyx. All other SUSARs will be submitted to the FDA, IRB and Ultragenyx within 15-calendar days of first knowledge of the event. Reports shall not be delayed due to incomplete information, which can be supplied as follow-up at a later time. Sponsor-Investigator shall record non-serious adverse events per Institution's clinical procedures. Where there is any doubt or debate relating to whether an AE is serious or non-serious, the AE shall be treated as an SAE until information is received to clarify seriousness. Sponsor-Investigator shall cooperate with Ultragenyx in any request for information on SAE reporting related to the Protocol. Ultragenyx will not be responsible for reporting safety information from treatment of patient(s) by Sponsor-Investigator or Institution to the Health Authorities.

The following timeframes shall apply to both initial and follow-up reports unless otherwise specified:

Sponsor-Investigator shall send to Ultragenyx final copies of initial and follow-up SAE reports within the timeframes specified in [Table 4](#) using FDA MedWatch Form 3500A.

Table 4: Reporting Timeframe from Sponsor-Investigator to Ultragenyx

Type of Report	Reporting Timeframe from Sponsor-Investigator to Ultragenyx	Format
Suspected Unexpected Serious Adverse Reactions – Fatal and Life-threatening	Final report no later than 7 calendar days from Sponsor-Investigator event knowledge with an additional 8 calendar days for follow-up report.	FDA MedWatch 3500A)
Suspected Unexpected Serious Adverse Reactions – other serious criteria	Final report no later than 15 calendar days of Sponsor-Investigator event knowledge.	FDA MedWatch 3500A
Suspected Unexpected Serious Adverse Reactions – Follow-up reports	No later than 15 calendar days after Sponsor-Investigator receipt of follow-up information (see follow-up requirements above for fatal/life-threatening SUSAR)	FDA MedWatch 3500A
Non-SUSAR SAEs - regardless of relatedness to the Product	No later than 30 calendar days from Sponsor-Investigator event knowledge	FDA MedWatch 3500A and SAE line listing

Type of Report	Reporting Timeframe from Sponsor-Investigator to Ultragenyx	Format
Annual Safety Report	Provided in parallel with submission to regulatory authorities	Annual Safety Report

Ultragenyx shall provide the Institution and/or Sponsor-Investigator copies of SUSARs received from other clinical trials or expanded access using the same Investigational Product as specified in [Table 5](#).

Table 5: Reporting Timeframe from Ultragenyx to Institution and/or Sponsor-Investigator

Type of Report	Reporting Timeframe from Ultragenyx to Institution and/or Sponsor-Investigator	Format
Suspected Unexpected Serious Adverse Reactions – Fatal and Life-threatening*	No later than 7 calendar days from Ultragenyx event knowledge	FDA MedWatch 3500A
Suspected Unexpected Serious Adverse Reactions – other serious criteria*	No later than 15 calendar days from Ultragenyx event knowledge	FDA MedWatch 3500A
Suspected Unexpected Serious Adverse Reactions – Follow-up reports*	No later than 15 calendar days after Ultragenyx receipt of follow-up information	FDA MedWatch 3500A
Investigational Product Investigator Brochure (including safety attachments, as appropriate)	Within 15 calendar days of final update	Email to Sponsor-Investigator

*SUSARs from Ultragenyx-sponsored studies using the same Investigational Product (cross-reporting to Sponsor-Investigators)

Should Ultragenyx require additional information on a SAE, Ultragenyx may send a request to the Institution and Sponsor-Investigator for follow-up as appropriate. Institution and Sponsor-Investigator shall use reasonably diligent efforts to conduct follow up activities on SAE reports in accordance with their standard operating procedures and in compliance with all Applicable Laws.

Institution and Sponsor-Investigator shall transmit to Ultragenyx the information required pursuant to the above provisions by facsimile, e-mail or other agreed-upon electronic means. If the volume of pages is deemed too large for reasonable electronic transmission, the information will be sent by expedited courier service.

All SUSARs and SAEs shall be documented and provided to Ultragenyx/designee using the FDA MedWatch Form 3500A or CIOMS I form (non-US) within the timeframes set forth in [Table 4](#).

Contact information:

Ultragenyx Pharmaceutical/designee

eFax: [name]

email: [contact]

For other safety related correspondence including providing of annual safety reports:

Contact information:

Ultragenyx Drug Safety and Pharmacovigilance

eFax: [contact] or [name]

email: [contact]

The Sponsor-Investigator is also responsible for providing Ultragenyx all final SAE and SUSAR reports submitted to regulatory authorities via the contact information listed above. The report must be completed on a FDA MedWatch Form 3500A. Ultragenyx reserves the right to review SUSAR reports, SAE reports or source documents pertaining to Protocol safety reports in response to any regulatory authority inquiries received.

SUSARs shall not be considered addendums to the IB until a formal update to the IB is made by Ultragenyx.

As per Applicable Laws, the Institution and/or Sponsor-Investigator are responsible for the development and submission of annual safety reports to regulatory health authorities and IRBs as it pertains to the overall conduct of the specific Protocol. The Institution and/or Sponsor-Investigator shall provide Ultragenyx a copy of the annual safety report in parallel to its submission to regulatory authorities.

Ultragenyx shall provide the Institution and/or Sponsor-Investigator a copy of the IB and any revisions within the specified timeframe ([Table 5](#)).

Ultragenyx will be responsible for the conduct of surveillance and safety signal detection activity using the Global Safety Database and ad-hoc reports in accordance with Ultragenyx sponsored study procedures and will notify Sponsor-Investigator of safety signals that do, or may, affect the safety profile of the Investigational Product, taking into consideration the urgency of the matter and the Applicable Laws.

Ultragenyx and Sponsor-Investigator shall promptly inform each other of all adverse event information relating to Investigational Product, including but not limited to, safety issues that either party becomes aware of or material safety-related regulatory queries from regulatory authorities taking into consideration the urgency of the matter and the Applicable Laws. The Sponsor-Investigation will submit an IND Safety Report for any SUSARs, according to 21 CFR 312.32, when informed of such event by Ultragenyx. Ultragenyx may request assistance from Sponsor-Investigator to evaluate and investigate such safety information and Sponsor-Investigator undertakes to use reasonably diligent efforts to promptly investigate and respond to Ultragenyx's requests.

Sponsor-Investigator shall be solely responsible for regulatory submissions of AEs and SAEs in regards to the Sponsor-Investigator's regulatory health authority approval and IRB in accordance with the Applicable Laws.

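### Sections 5.1 and 5.1.1 define an expected event differently, so it is unclear whether a related serious event worse than the Investigator's Brochure describes is a SUSAR

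*Combined protocol and SAP*

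**What the plan says.** Section 5.1 (Adverse Events Monitoring) defines an unexpected adverse event as "any adverse experience for which the specificity or severity of the event is not consistent with the current IB".

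Section 5.1.1 (Reporting of Serious Adverse Events) uses a different test. It says "Events not listed in the Investigator Brochure (IB) are considered 'unexpected", and continues "and events listed in the IB are considered 'expected". The sentence carries no qualifier on severity or specificity. Shortly afterwards comes the reporting trigger: "All SAEs considered by the Sponsor-Investigator as unexpected per the IB, and Investigational Product related, must be reported as a SUSAR", to be done "by the Sponsor-Investigator to the FDA and IRBs in accordance with Applicable Laws".

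Other text in Section 5.1.1 bears on how the trigger is read:

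- SUSAR reporting to the IRB and the FDA is to be "in accordance with 21 CFR 312.32, in connection with the Protocol".
- A separate duty covers "SAEs meeting SUSAR criteria, as defined by Applicable Laws and regulations" that occur during treatment. These go to the FDA and to the supplier (Ultragenyx) within 15 calendar days.
- SAE procedures add to those of Section 5.1: "In addition to the above procedures for AEs, all SAEs will be reported to the IRB within 24 hours of recording".

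**The concern.** For a related SAE, the expectedness call decides whether it becomes a SUSAR. The two sections give opposite calls for one kind of event: serious, related, named in the IB, but more severe or more specific than the IB describes. The listing rule stands in the reporting section beside the trigger, so staff classifying an SAE are likely to reach for it.

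The main exposure is expedited reporting to the FDA. If the event is classed as expected, the next scheduled safety report to the FDA that the protocol names is the annual one, whose content is not specified. Timing to the supplier comes second.

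There is little else to catch a misclassification on that path. Section 5.2 states that there is no DSMB, formal safety monitoring plan or formal stopping rule. Section 5.1.1 makes the Sponsor-Investigator solely responsible for regulatory submissions. Its rule for doubtful cases covers only serious versus non-serious, not expected versus unexpected.

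**Working it through.** No statistical calculation applies. The check sets the two definitions side by side and then follows the protocol's own reporting clocks.

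**Step 1. Classify a related SAE under each rule.**

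| Event | Section 5.1 (consistency with IB) | Section 5.1.1 (listing) | Agree? |
|---|---|---|---|
| Not in the IB | Unexpected | Unexpected | Yes |
| In the IB, specificity and severity as described | Expected | Expected | Yes |
| In the IB, but more severe or more specific than described | Unexpected | Expected | **No** |

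Only the third row conflicts, so only the second half of the Section 5.1.1 sentence causes the problem.

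**Step 2. Follow the third row through the reporting clocks.** Inputs are the SUSAR timeframes in the text of Section 5.1.1 and the supplier timeframes in its Table 4, in calendar days from knowledge of the event.

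| Recipient and event | SUSAR (Section 5.1 definition) | Not a SUSAR (listing sentence taken alone) | Difference |
|---|---|---|---|
| FDA and IRB SUSAR report, fatal or life-threatening | Day 7, follow-up by day 7 + 8 = 15 | Not triggered by that sentence | Report depends on the reading |
| FDA and IRB SUSAR report, other serious | Day 15 | Not triggered by that sentence | Report depends on the reading |
| Supplier, other serious | Day 15 | Day 30 (non-SUSAR row) | 30 − 15 = 15 days on the Table 4 limit |
| Supplier, fatal or life-threatening during treatment | Day 7 | Day 7, whatever the expectedness | 7 − 7 = 0 |
| IRB, first SAE notice | 24 hours from recording | 24 hours from recording | 0 |

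**Step 3. List the routes that do not depend on expectedness.**

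- IRB: every SAE within 24 hours of recording, and further SAE notification under IRB requirements and applicable law (both Section 5.1.1); prompt reporting of all adverse events (Section 5.2).
- Supplier: fatal or life-threatening SAEs during treatment within 7 days, and a mutual duty to share all adverse event information promptly (both Section 5.1.1). Table 4's 30 days is therefore an outer limit for the formal report, not the only way the supplier learns of the event.
- FDA: no notice of individual events that is stated to apply whatever the expectedness.

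**Step 4. Look for text that settles the conflict.** The citation of 21 CFR 312.32, the legally defined SUSAR criteria and the general duty to comply with applicable law on SAE reporting all point outside the protocol. None reproduces a definition of unexpected. None says that the law, or Section 5.1, overrides the listing sentence. Section 5.1.1 also has expectedness recorded under the institution's policies, a further standard whose content is not given.

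**The case against.** The best defence is that the listing sentence should not be read in isolation. Section 5.1.1 has its own mandatory duty to send SAEs that meet legally defined SUSAR criteria during treatment to the FDA and the supplier within 15 days. That duty does not take its criteria from the listing sentence. The section cites 21 CFR 312.32, requires compliance with all applicable law on SAE reporting, and gives the institution or Sponsor-Investigator the task of deciding whether each SAE is reportable. A harmonised reading is also open: SAE procedures add to those of Section 5.1, and listed can be taken to mean listed as described.

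Much of this stands. A reader might infer that the FDA would receive no expedited report of such an event, and that the supplier would always be told 15 days later. The documents do not support that. Both results follow only if the listing sentence is applied alone, and the separate duty may bring the same event back in. Whether it does depends on the content of a regulation that the documents do not reproduce, so neither outcome can be asserted. Nor would it be right to infer that the IRB is left uninformed: it receives the first SAE notice on the same clock either way, and what could be lost is the formal SUSAR report.

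What does not stand is the suggestion that the conflict is thereby resolved. A general duty to comply with the law does not tell staff which of two stated definitions to apply while a 7- or 15-day clock runs.

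**Conclusion.** The two definitions contradict each other for one class of event, and nothing in the protocol says which governs. That much follows directly from the text. The consequence is ambiguity over reporting, not a demonstrated loss of reports. The main exposure is the expedited report to the FDA (7 or 15 days, or not triggered by the listing sentence). After that comes the Table 4 limit to the supplier for other serious events (15 or 30 days). The IRB's first notice and the supplier's notice of fatal or life-threatening SAEs during treatment are unchanged.

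The number of affected events cannot be estimated, because the IB is not among the documents. Ten people with ALS are planned for treatment. No endpoint, sample size or analysis is affected. The change should be made: a stated rule can misclassify a serious related event, and the repair is small.

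**What to change.** Reconcile the two sections on a single definition. Leave the first half of the Section 5.1.1 sentence, on unlisted events, as it stands. Amend the second half so that a listed event counts as expected only if both its specificity and its severity are consistent with the current IB, with a cross-reference to Section 5.1. The third row of the first table then reads the same under both sections, and the SUSAR trigger needs no change.

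The cost is half a sentence, and possibly a few more expedited reports. Visits, endpoints, sample size and analysis stay as they are.
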